**13. Study Flow Chart**

This is a multicenter Italian randomized clinical study in which patients with MINOCA will be enrolled after a careful check of the inclusion and exclusion criteria. The flow chart of the study is resumed in the following **Figure** and schematized in the next sections:

\*Patients with Takotsubo syndrome and myocarditis (based on clinical history and CMR) will be excluded from the study.

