### **11a. Intervention(s):**

Patients with myocardial infarction undergoing to clinically indicated coronary angiography will be asked to sign the informed consent to the study before the coronary angiography/ventriculography and enrolled only after MINOCA diagnosis. MINOCA patients will be then randomized 1:1 (using an online software available 24h/24h) to:

**A. "Precision medicine approach"** consisting of:

*Comprehensive diagnostic work-up with:*

- Coronary angiography and ventriculography in all patients
- OCT (if coronary plaque rupture/erosion is suspected) at the time of coronary angiography in the cath-lab.
- Acetylcholine provocative test (to assess the presence of coronary vasospasm) at the time of coronary angiography in the cath-lab.
- TE-Echo and/or CE-Echo (if distal/microvascular embolization is suspected) during the hospitalization at the echo laboratory
- Blood sampling for circulating biomarkers and miRNA expression profile at the time of coronary angiography or within 12 hours from coronary angiography. Blood sampling will be processed and analysed in the research laboratory of the Department of Cardiovascular Science. Biological aliquots will be preserved at XBiogem Biobank at Fondazione Policlinico Universitario A. Gemelli IRCCS, Rome.
- Trans-thoracic echocardiography in all patients during the index hospitalization
- CMR in all cases during the index hospitalization.

*Targeted pharmacological treatment specific for the underlying cause:*

- DAPT ± stent implantation (if required), statins, beta-blockers, ACEi/ARB (in case of evidence of plaque rupture/erosion)
- CCB and/or nitrates (in case of documentation of coronary vasospasm)
- Anticoagulation (in case of coronary embolism).

**B. "Standard approach"** consisting of:

*Routine diagnostic work-up with:*

- Coronary angiography and ventriculography
- Transthoracic echocardiography in all patients during the index hospitalization
- CMR with contrast media only if clinically indicated (i.e. to exclude myocarditis or takotsubo syndrome)

*Standard medical treatment with:*

- DAPT in all patients
- Beta-blockers (if indicated by the clinical context, i.e. documentation of left ventricular ejection fraction <50%, tachycardia).

- High intensity statins in all patients
- ACEi/ARB (if clinically indicated).

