- *Cardiac magnetic resonance*: CMR will be performed during hospital stay on a 1.5-T system equipped with a 32-channel cardiac coil. Patients underwent conventional CMR including cine, T2-weighted, first pass perfusion, and conventional breath-held late gadolinium enhancement (LGE).
- *Circulating biomarkers*: Blood sampling for circulating biomarkers and miRNA expression profile at the time or within 12 hours of coronary angiography. Blood sampling will be processed and analysed in the research laboratory of the Department of Cardiovascular

Science. Biological aliquots will be preserved at XBiogem Biobank at Fondazione Policlinico Universitario A. Gemelli IRCCS, Rome (see section 33).

*Risk analysis, possible problems and solutions:*

- OCT is a safe invasive intracoronary imaging tool. Complications during manipulation inside coronary arteries are rare. This procedure will be performed by experienced operators to improve its safety.
- CMR with intravenous gadolinium administration is a safe procedure, associated with a low risk of renal damage, also in patients with severe kidney disease, and allergic reactions. These side effects may, however, be prevented and treated appropriately.
- A transesophageal echocardiogram (TEE) uses echocardiography to assess the structure and function of the heart. It is associated with a rare risk of complication, such as bleeding, airway difficulty, arrhythmias and local trauma. The risk of complications will be reduced by using an experienced sonographer and by excluding patients with Echo TE contraindications (oesophageal varices, oesophageal obstruction or stricture, or radiation therapy to the area of the esophagus). Contrast echocardiography refers to diagnostic ultrasound of the heart that is performed in conjunction with any acoustically active particle, including agitated saline and is not associated with any complication.

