***T4\_ Follow-up clinical visit at 12 months (365 +/- 5 gg)***

- Personal information: weight, height, BMI
- Collection of ongoing medical therapy
- Compilation of SAQ score
- Collection of MACE at follow-up
- Registration of adverse events

Study Assessment	Screening and randomization	Follow-up phone interview_ T1 (3 months)	Follow-up phone interview_ T2 (6 months)	Follow-up phone interview_ T3 (9 months)	Visit of End of Follow-up (12 months)
Days	0	90 +/- 5 gg	180 +/- 5 gg	270 +/- 5 gg	365 +/- 5 gg
Weeks	0	12	24	36	52

Informed consent	X				
Inclusion criteria	X				
Anagraphic data	X				
Personal information (weight, height,BMI)	X				X
Clinical history	X				
Clinical examination	X				
Vital signs	X				
Ongoing medical therapy (concomitant medications included)	X	X	X	X	X
Patients assigned to "Standard approach"	X				
ECG features	X				
Transthoracic Echocardiography	X				
Coronary angiography and ventriculography	X				
CMR with contrast media (if clinically indicated)	X				
Laboratory data (creatinine, full blood count, Troponin I peak, CK-MB peak, NTproBNP, CRP)	X				
Patients assigned to "Precision-medicine approach"					
OCT (if coronary plaque rupture/erosion is suspected)	X				
	X				

Acetylcholine provocative test (to assess the presence of coronary vasospasm)					
TE-Echo and/or CE-Echo (if distal/microvascular embolization is suspected)	X				
CMR with contrast media (if clinically indicated)	X				
Blood sampling for circulating biomarkers and miRNA expression profile	X				
Collection of MACE	X	X	X	X	X
Adverse events	X	X	X	X	X
SAQ score					X

SAQ score:

1. The following is a list of activities that people often do during the week. Although for some people with several medical problems it is difficult to determine what it is that limits them, please go over the activities listed below and indicate how much limitation you have had **due to chest pain, chest tightness, or angina over the past 4 weeks.**

Place an x in one box on each line.

Activity	Severely Limited	Moderately Limited	Somewhat Limited	A Little Limited	Not Limited	Limited, or did not do for other reasons
Dressing yourself						

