## **METHODS: INTERVENTION ALLOCATION**

### **16-17 Randomization**

Trained staff in the catheter laboratory will use a web-based randomization tool, available 24h/24h at any of the enrolling sites, to immediately randomize the patient after the index coronary angiography revealing non obstructive CAD, to “precision medicine approach” versus “standard approach” (open label approach: both patients and physicians will know the allocated treatment arm).

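### CMR-based exclusion of myocarditis and takotsubo can follow randomisation at an arm-dependent rate, and no rule keeps re-diagnosed patients in follow-up and analysis

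*Combined protocol and SAP*

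**What the plan says.** **Order of events.** Section 16-17 has catheter-laboratory staff use a web tool "to immediately randomize the patient after the index coronary angiography revealing non obstructive CAD". The same section describes the trial as "open label approach: both patients and physicians will know the allocated treatment arm". Section 11a places the acetylcholine test, a precision-arm procedure, in that same session, so allocation must already be known then. Under Interventional Procedures, "CMR will be performed during hospital stay".

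**CMR by arm.** For the precision arm Section 11a lists "CMR in all cases during the index hospitalization", and the T0 list in the Study Timeline also gives it without condition. For the standard arm Section 11a lists "CMR with contrast media only if clinically indicated (i.e. to exclude myocarditis or takotsubo syndrome". The assessment table at the end of the timeline disagrees about the precision arm: its row there reads "CMR with contrast media (if clinically indicated".

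**Exclusion.** The note in Section 13 states that "Patients with Takotsubo syndrome and myocarditis (based on clinical history and CMR) will be excluded from the study", with no timing. The exclusion criteria also rule out myocarditis and takotsubo without timing. Section 11a says patients are "enrolled only after MINOCA diagnosis".

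**Handling afterwards.** The withdrawal criteria do not name re-diagnosis. Section 20 defines the study population by informed consent and compares randomised groups. It does not say that patients are analysed as randomised, or that follow-up continues after a change of diagnosis. Section 12 defines the primary endpoint in patients with MINOCA.

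**The concern.** A CMR that is assigned by arm cannot inform a decision taken before allocation. Exclusion that rests on it can only happen after randomisation, and more readily in the arm where everyone is scanned. In controls, the scan depends on the judgement of physicians who know the allocation.

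If exclusion means no 12-month SAQ or removal from the analysis, the precision arm becomes a largely CMR-cleared group, while controls keep the mimics that nobody looked for. The primary SAQ comparison and the MACE comparison would then lose the protection of randomisation. The schedule collects the SAQ only at 12 months, so a questionnaire not obtained from an excluded patient cannot be recovered later.

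Removal would also use up the sample-size allowance, which Section 14 justifies only by loss to follow-up and poor compliance.

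**Working it through.** **The plan's own figure.** Section 14 uses a 9 U difference, SD 19 U, two-sided 5% and 80% power. The normal formula gives n = 2 × 19² × (1.960 + 0.842)² / 9² = 69.96, so 70 per arm (140 in total), as stated. The t-test version gives 71. The extension to 180 allows (180 − 140)/2 = 20 losses per arm. The sample size is not in dispute.

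**Assumptions.** The documents give no mimic rate, no control detection rate and no SAQ difference between mimics and true MINOCA. I take:
- p = share of mimics among randomised patients, 10–30%;
- detection in the precision arm = 100%;
- q = share of true mimics detected in controls, 10–80%;
- D = SAQ difference between mimics and true MINOCA, 10 U (range 5–15 U);
- every detected mimic is removed.

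**Formulas**, with 90 randomised per arm:
- Residual mimic share in controls: r = p(1 − q)/(1 − pq)
- Shift in the group difference: r × D
- Extra removals in the precision arm: 90p(1 − q)

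| p | q | r | Shift at D = 10 U | Removed, precision vs control | Extra removals |
|---|---|---|---|---|---|
| 10% | 80% | 2.2% | 0.22 U | 9.0 vs 7.2 | 1.8 |
| 10% | 50% | 5.3% | 0.53 U | 9.0 vs 4.5 | 4.5 |
| 20% | 80% | 4.8% | 0.48 U | 18.0 vs 14.4 | 3.6 |
| 20% | 50% | 11.1% | 1.11 U | 18.0 vs 9.0 | 9.0 |
| 20% | 30% | 14.9% | 1.49 U | 18.0 vs 5.4 | 12.6 |
| 30% | 50% | 17.6% | 1.76 U | 27.0 vs 13.5 | 13.5 |
| 30% | 10% | 27.8% | 2.78 U | 27.0 vs 2.7 | 24.3 |

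At D = 10 U the shift is 0.22/9 = 2% to 2.78/9 = 31% of the target difference. Over D = 5–15 U it runs from 0.11 to 4.18 U.

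**Type I error.** With no true effect, SE = 19 × √(1/n_P + 1/n_S), where n_P = 90(1 − p) and n_S = 90(1 − pq). At q = 50% and D = 10 U, the two-sided error is 5.4%, 6.5% and 8.5% for p = 10%, 20% and 30%. At p = 5% and q of 20% or more it is at most 5.5% even with D = 15 U, which is negligible.

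**Allowance.** At p = 20% the precision arm keeps 90 − 18 = 72 patients. That uses 18 of its 20 spare places before any loss to follow-up.

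**The case against.** The strongest reply is that no sentence says a randomised patient is removed after CMR. The exclusion sentence is a note to a figure not available here, and it may belong to the screening step. Section 13 speaks of a careful check of the criteria before enrolment, and Section 11a of enrolment after diagnosis. Section 20 compares randomised groups, which leans towards keeping patients where they were allocated. Clinical history and ventriculography are available in both arms, and the control-arm indication for CMR is the very suspicion at issue, so detection in controls may be high. If the assessment table governs, the arm difference in CMR could shrink or vanish. The larger figures come from one corner of an assumed grid.

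Much of this stands as a limit on size. Post-randomisation removal is inferred from the timing, the bias is conditional, and the mid-range figures are modest. It does not remove the point. Exclusion before enrolment may well have been the intention, but it cannot work for a scan that is assigned by allocation. Comparing randomised groups does not settle who stays in them or who is followed. Because consent precedes angiography, a population defined by consent also includes people never randomised, so it is not an as-randomised rule. Even if the table governs, open-label ordering of CMR after randomisation remains.

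A further fair objection is that keeping patients with proven myocarditis or takotsubo moves the analysed population towards MINOCA as diagnosed at angiography. That is a real choice of estimand, and the plan should state it.

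**Conclusion.** The concern holds. As written, the plan allows exclusion after randomisation with a probability that depends on the arm, and it has no rule that keeps re-diagnosed patients in follow-up and analysis. This should be fixed.

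The plan does not show that bias will occur. If patients are removed, the illustrative shift at a 10 U difference is 0.5–1.8 U with half of control mimics detected, and 0.2–2.8 U over the full range of control detection. The precision arm would lose about 2–24 more patients than controls. These figures rest on assumed rates of mimics and detection and an assumed SAQ difference. The direction cannot be found from the documents. The shift is zero if everyone is retained and followed, or if detection is equal in both arms.

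**What to change.** 1. In Section 20, define the primary analysis set as all randomised patients, analysed in the assigned arm. Require follow-up to the 12-month SAQ and MACE assessment whatever a later CMR shows. This rule concerns data collection and analysis and leaves clinical care unaffected.
2. State that exclusion from the trial rests only on findings available before randomisation in both arms. Align the inclusion and exclusion criteria (Section 10), Section 12 and the Section 13 note with this.
3. Report CMR re-diagnoses by arm. Label any analysis restricted to CMR-confirmed MINOCA as a sensitivity analysis.
4. Reconcile Section 11a and the T0 list with the assessment table on CMR in the precision arm.

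An eligibility assessment that is identical in both arms and blind to allocation would also remove the bias. It needs the same CMR information in controls, however, and so changes the comparator.

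**Cost.** Wording only, with no added procedures. The statistical cost is possible dilution. If a share p of patients gains nothing, the effect becomes 9(1 − p). Two-sample t-test, SD 19 U, two-sided 5%:

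| Share with no gain | Effect | Power, 90 completers per arm | Power, 70 completers per arm | Completers per arm for 80% |
|---|---|---|---|---|
| 0% | 9.0 U | 88.5% | 79.5% | 71 |
| 10% | 8.1 U | 81.2% | 70.7% | 88 |
| 20% | 7.2 U | 71.5% | 60.5% | 111 |

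The power statement in Section 14 should give this range.

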## Study timeline

# Study Timeline

### *T 0 (index hospitalization for MINOCA):*

During the index hospitalization the study investigators, after a careful evaluation of the inclusion and exclusion criteria of the patients, will collect:

- Anagraphic data
- Personal information: weight, height, BMI
- Vital parameters (blood pressure, heart rate, oxygen saturation)
- Therapy at admission and at discharge (concomitant medications included)
- Cardiovascular risk factors: family history of early coronary artery disease (first degree relative with a history of myocardial infarction <60 years), diabetes mellitus [fasting blood glucose >126 mg/dL or treated diabetes mellitus (intake of a diabetic diet or oral hypoglycaemic agents), according to the American Diabetes Association (ADA) criteria], hypercholesterolemia (total cholesterol >200 mg/dL or treated hypercholesterolemia), smoking (current), and hypertension (systolic blood pressure >140 mmHg and/or diastolic blood pressure >90 mmHg or treated hypertension).

- Relevant comorbidities: anaemia, chronic kidney disease, atrial fibrillation, history of stroke/TIA, peripheral vascular disease
- ECG features (ST segment elevation/depression or T wave inversions, atrioventricular blocks, arrhythmias)
- Trans-thoracic color-Doppler echocardiography (chamber volumes, systolic and diastolic function)
- Data on coronary angiography and ventriculography (presence/absence of non-obstructive CAD, micro vs epicardial coronary spasm, “hazy” angiographic images, TIMI flow, LVEDP)
- Laboratory data (creatinine, full blood count, Troponin I peak, CK-MB peak, NT-proBNP, CRP)

For patients randomized to “*precision medicine approach*”:

- OCT (if coronary plaque rupture/erosion is suspected) at the time of coronary angiography in the cath-lab.
- Acetylcholine provocative test (to assess the presence of coronary vasospasm) at the time of coronary angiography in the cath-lab.
- TE-Echo and/or CE-Echo (if distal/microvascular embolization is suspected) during the hospitalization at the echo laboratory
- CMR with contrast media: anatomical and morphological data
- Blood sampling for circulating biomarkers and miRNA expression profile at the time or within the 12 hours from coronary angiography. Blood sampling will be processed and analysed in the research laboratory of the Department of Cardiovascular Science. Biological aliquots will be preserved at XBiogem Biobank at Fondazione Policlinico Universitario A. Gemelli IRCCS, Rome.

For patients randomized to *Routine diagnostic work-up*:

- Coronary angiography and ventriculography
- Transthoracic echocardiography in all patients during the index hospitalization
- CMR with contrast media only if clinically indicated (i.e. to exclude myocarditis or takotsubo syndrome)

***T1\_ Follow-up phone interview at 3 months (90 +/- 5 gg)***

- Collection of MACE at follow-up
- Collection of ongoing medical therapy
- Registration of adverse events

***T2\_ Follow-up phone interview at 6 months (180 +/- 5 gg)***

- Collection of MACE at follow-up
- Collection of ongoing medical therapy
- Registration of adverse events

***T3\_ Follow-up phone interview at 9 months (270 +/- 5 gg)***

- Collection of MACE at follow-up
- Collection of ongoing medical therapy
- Registration of adverse events

***T4\_ Follow-up clinical visit at 12 months (365 +/- 5 gg)***

- Personal information: weight, height, BMI
- Collection of ongoing medical therapy
- Compilation of SAQ score
- Collection of MACE at follow-up
- Registration of adverse events

Study Assessment	Screening and randomization	Follow-up phone interview_ T1 (3 months)	Follow-up phone interview_ T2 (6 months)	Follow-up phone interview_ T3 (9 months)	Visit of End of Follow-up (12 months)
Days	0	90 +/- 5 gg	180 +/- 5 gg	270 +/- 5 gg	365 +/- 5 gg
Weeks	0	12	24	36	52

Informed consent	X				
Inclusion criteria	X				
Anagraphic data	X				
Personal information (weight, height,BMI)	X				X
Clinical history	X				
Clinical examination	X				
Vital signs	X				
Ongoing medical therapy (concomitant medications included)	X	X	X	X	X
Patients assigned to "Standard approach"	X				
ECG features	X				
Transthoracic Echocardiography	X				
Coronary angiography and ventriculography	X				
CMR with contrast media (if clinically indicated)	X				
Laboratory data (creatinine, full blood count, Troponin I peak, CK-MB peak, NTproBNP, CRP)	X				
Patients assigned to "Precision-medicine approach"					
OCT (if coronary plaque rupture/erosion is suspected)	X				
	X				

Acetylcholine provocative test (to assess the presence of coronary vasospasm)					
TE-Echo and/or CE-Echo (if distal/microvascular embolization is suspected)	X				
CMR with contrast media (if clinically indicated)	X				
Blood sampling for circulating biomarkers and miRNA expression profile	X				
Collection of MACE	X	X	X	X	X
Adverse events	X	X	X	X	X
SAQ score					X

SAQ score:

1. The following is a list of activities that people often do during the week. Although for some people with several medical problems it is difficult to determine what it is that limits them, please go over the activities listed below and indicate how much limitation you have had **due to chest pain, chest tightness, or angina over the past 4 weeks.**

Place an x in one box on each line.

Activity	Severely Limited	Moderately Limited	Somewhat Limited	A Little Limited	Not Limited	Limited, or did not do for other reasons
Dressing yourself						
Walking indoors on level ground						
Showering						
Climbing a hill or a flight of stairs without stopping						
Gardening, vacuuming, or carrying groceries						
Walking more than a block at a brisk pace						
Running or jogging						
Lifting or moving heavy objects (e.g. furniture, children)						
Participating in strenuous sports (e.g. swimming, tennis)						

2. Compared with 4 weeks ago, how often do you have **chest pain, chest tightness, or angina** when doing your **most strenuous** level of activity?

I have had **chest pain, chest tightness, or angina**...

Much more often	Slightly more often	About the same	Slightly less often	Much less often
				

**3. Over the past 4 weeks, on average, how many times have you had chest pain, chest tightness, or angina?**

**I get chest pain, chest tightness, or angina...**

4 or more times per day	1-3 times per day	3 or more times per week but not every day	1-2 times per week	Less than once a week	None over the past 4 weeks
					

**4. Over the past 4 weeks, on average, how many times have you had to take nitros (nitroglycerin tablets) for your chest pain, chest tightness, or angina?**

**I take nitros...**

4 or more times per day	1-3 times per day	3 or more times per week but not every day	1-2 times per week	Less than once a week	None over the past 4 weeks
					

5. How bothersome is it for you to take your pills for **chest pain, chest tightness or angina** as prescribed?

Very bothersome	Moderately bothersome	Somewhat bothersome	A little bothersome	Not bothersome at all	My doctor has not prescribed pills
					

6. How satisfied are you that everything possible is being done to treat your **chest pain, chest tightness, or angina**?

Not satisfied at all	Mostly dissatisfied	Somewhat satisfied	Mostly satisfied	Highly satisfied
				

7. How satisfied are you with the explanations your doctor has given you about your **chest pain, chest tightness, or angina**?

Not satisfied at all	Mostly dissatisfied	Somewhat satisfied	Mostly satisfied	Highly satisfied
				

8. Overall, how satisfied are you with the current treatment of your **chest pain, chest tightness, or angina**?

Not satisfied at all	Mostly dissatisfied	Somewhat satisfied	Mostly satisfied	Highly satisfied
				

9. Over the past 4 weeks, how much has your **chest pain, chest tightness, or angina** interfered with your enjoyment of life?

It has severely limited my enjoyment of life	It has moderately limited my enjoyment of life	It has slightly limited my enjoyment of life	It has barely limited my enjoyment of life	It has not limited my enjoyment of life
				

10. If you had to spend the rest of your life with your **chest pain, chest tightness, or angina** the way it is right now, how would you feel about this?

Not satisfied at all	Mostly dissatisfied	Somewhat satisfied	Mostly satisfied	Highly satisfied
				

i i. How often do you worry that you may have a heart attack or die suddenly?

I can't stop worrying about it	I often think or worry about it	I occasionally worry about it	I rarely think or worry about it	I never think or worry about it
				

